3.6 Safety analysis

Safety assessment will be based on AEs and oral inspections recorded at each visit.

All AEs will be coded using coding dictionaries MedDRA version 16.0 or higher and will be summarized by system organ class and preferred term. AEs will be described by seriousness, onset and resolution dates, duration, severity, pattern, action taken, relationship to the study drug and outcome.

The primary safety evaluation of the PerioChip® will be performed by comparison to the Subgingival debridement treatment. Specifically, the number of AEs reported for each treatment group will be compared to see if there is a treatment-related difference in the appearance of the following:

1. Number of dental-related AEs, such as dental or gingival pain.
2. Observed changes in the clinical appearance of the tissues at each of the oral inspections relative to baseline.

The number of dental-related AEs reported and the time of first occurrence of dental-related events will be evaluated to assess if the event is associated with the chip insertion. In addition, all other reported AEs will be evaluated for any treatment related effects. To clarify, AEs that were reported more than once by a subject during the same period will be counted only once for that subject and period at the maximum severity.

Chi-square test or Fisher's Exact test will be applied for testing the above differences between the groups.

Oral inspections will evaluate any changes from baseline in the target implant/s that can be attributed to treatment.

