All treatment comparison will be two-sided at the 0.05 level of significance.

The data will be analyzed using the SAS® version 9.3 (SAS Institute, Cary North Carolina) or higher version.

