14.3 Safety Data

14.3.1-1	Summary Incidence and Frequency of Adverse Events by Treatment (ITT) (Part 1 of 2)
14.3.1-1	Summary Incidence and Frequency of Adverse Events by Treatment (ITT) (Part 2 of 2)
14.3.1-2	Adverse Events by SOC and PT (ITT)
14.3.1-3	Adverse Events by SOC, PT and relationship to study drug (ITT)
14.3.1-4	Adverse Events by SOC, PT and severity (ITT)
14.3.2	Listings of Deaths, other serious and significant AEs
14.3.2-1	Serious Adverse Events
14.3.3	Other Safety Assessments
14.3.3-1	Oral Inspection and Treatment Results by Visit
14.3.3-2	Pocket Examination at Screening (All pockets, by-patient)

Table number	Table Title
14.3.3-3	Pocket Examination at Screening (All pockets, by-implant)
14.3.3-4	Pocket Examination at Baseline 6-8 mm in depth (All pockets, by-patient)
14.3.3-5	Pocket Examination at Baseline 6-8 mm in depth (All pockets, by-implant)
14.3.3-6	Plaque and Gingival Exam by visit
14.3.3-7	Pregnancy test results by visit
14.3.3-8	Oral Hygiene Instruction by visit
14.3.3-9	Supra-gingival scaling, Supra-gingival plaque removal and Sub-gingival debridement by Visit
14.3.3-10	Chip Insertion by visit
14.3.3-11	Any change in AE since last visit
14.3.3-12	Any dental change since last visit
14.3.3-13	Any change in concomitant medication since last visit
14.3.3-14	Any Concomitant medications

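### SAP 3.6 applies chi-square or Fisher's exact test to numbers of AEs and removes repeats only within an undefined period, so one patient can supply several records and the 5% test can be anti-conservative

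*SAP*

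**What the plan says.** SAP 3.6 makes the comparison with debridement alone the primary safety evaluation. The quantity compared is a count of events: "the number of AEs reported for each treatment group will be compared to see if there is a treatment-related difference". Two items follow. The first is "Number of dental-related AEs, such as dental or gingival pain". The second is change in tissue appearance from baseline at each oral inspection.

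The only rule on repeats is that "AEs that were reported more than once by a subject during the same period will be counted only once for that subject and period", at maximum severity. The test is then given: "Chi-square test or Fisher's Exact test will be applied for testing the above differences between the groups". SAP 2.1 adds that "All treatment comparison will be two-sided at the 0.05 level of significance".

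Three things are not stated: what a period is, whether the 2x2 table counts patients, patient-periods or events, and what the denominator is. The AE tables in Appendix I do not settle this. The title of Table 14.3.1-1 names both incidence and frequency and does not say which is tested.

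**The concern.** Chi-square and Fisher's exact test assume that the entries in the table are independent, which here means one entry per patient. The SAP's counting rule does not guarantee that. It collapses repeats inside a period, but a patient can count again in another period, or in the same period with a different dental AE.

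Repeats are plausible. In one arm a chip is inserted every fortnight for the first 12 weeks, and SAP 3.6 itself wants to learn whether dental AEs are linked to insertion. A patient who reacts to insertion may report pain after several visits. If each report is a separate entry, a few such patients weigh as much as many patients with one event each. The variance is then understated and the p-value is too small.

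This concerns the comparison that the SAP names as its primary safety evaluation. Two analysts could follow the text faithfully and report different p-values.

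**Working it through.** **The plan's own figure.** There is none to reproduce. The documents give no AE rate, no power for an AE comparison and no within-patient correlation.

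**Inputs from the documents**
- 290 patients randomized (SAP 1.8), so 290 / 2 = 145 per arm with equal allocation.
- 10 visits (SAP 1.2). Without screening and baseline, 10 - 2 = 8 remain, which is the natural count if a period is the interval between visits.
- Two-sided 5% level (SAP 2.1).

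**Inputs assumed**
- K, the number of yes/no AE records that each patient contributes to the table: 1, 3 or 8.
- Probability of an AE per record: 8%.
- Within-patient correlation rho: 0 to 0.3.

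**Formula.** If K records per patient are pooled and treated as independent, the true variance of the difference exceeds the assumed variance by the design effect

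DEFF = 1 + (K - 1) x rho.

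The actual type I error of the nominal 5% test is then

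2 x [1 - Phi(1.96 / sqrt(DEFF))].

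**Results**

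| K | rho | DEFF | 1.96 / sqrt(DEFF) | Type I error |
|---|---|---|---|---|
| 1 | any | 1.00 | 1.960 | 5.0% |
| 3 or 8 | 0 | 1.00 | 1.960 | 5.0% |
| 3 | 0.05 | 1.10 | 1.869 | 6.2% |
| 3 | 0.1 | 1.20 | 1.789 | 7.4% |
| 3 | 0.2 | 1.40 | 1.656 | 9.8% |
| 3 | 0.3 | 1.60 | 1.549 | 12.1% |
| 8 | 0.05 | 1.35 | 1.687 | 9.2% |
| 8 | 0.1 | 1.70 | 1.503 | 13.3% |
| 8 | 0.2 | 2.40 | 1.265 | 20.6% |
| 8 | 0.3 | 3.10 | 1.113 | 26.6% |

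**Check by simulation.** I simulated 20,000 trials per row under no treatment difference, with 145 patients per arm, beta-binomial records and Pearson chi-square without continuity correction. At an AE probability of 8% the pooled test rejected in 6.3% to 12.2% of trials for K = 3, and in 9.2% to 26.8% for K = 8, as rho went from 0.05 to 0.3. With K = 1 or rho = 0 it rejected in 4.5% to 5.0%. Runs with AE probabilities of 5%, 10% and 20% also followed the formula closely, so the AE rate matters little beside K and rho.

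**The patient-level alternative.** In the same simulated data, chi-square on patients with at least one AE rejected in 4.5% to 5.3% of trials, whatever K and rho.

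**The case against.** The strongest reply is that SAP 3.6 never describes a test on patient-periods. A 2x2 table needs non-events as well as events, and the denominator of patients times periods used above is not in the SAP. A table of patients with and without the AE needs no such addition.

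Several features favour that reading. The trial is a parallel two-arm design without formal treatment periods. The AE tables in Appendix I are split by treatment, SOC/PT, relationship and severity, and not by visit, although several other safety tables there are labelled as by visit. Incidence is to be tabulated as well as frequency. Counting once at maximum severity is a common way to reduce repeat reports to one record per subject. The protocol's change summary uses the word period for the whole study in its section 5.3, but for the interval between two visits in 6.2.2.

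Much of this stands. A reader might infer that the planned test is invalid. The documents do not support that: if the period is the whole study and the test is run separately for each AE category, the rule leaves at most one record per patient and the test keeps its level. A reader might also blame the once-per-period rule. That rule lessens dependence; the problem is what remains across periods and terms.

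The reply does not remove the point. The quantity named for testing is a number of AEs, nothing in 3.6 says patients with at least one AE, and a rule per subject and period would hardly need its second element if there were only one period. Nor does a study-long period stop a patient from counting under two dental terms.

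For the oral inspections, a comparison made separately at each inspection does not pool visits. The unit is still unstated, and a patient may have two target implants.

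**Conclusion.** The point holds conditionally. Followed literally, SAP 3.6 lets one patient supply several non-independent records to a chi-square or Fisher test, which can then be anti-conservative. On the assumed inputs, type I error is about 6-12% with 3 records per patient and 9-27% with 8, against 5% intended. There is no inflation with one record per patient or zero correlation.

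The size rests on the number of records, the AE probability and the correlation, none of which the documents give. It would therefore be wrong to state outright that the safety p-values will be too small. What is certain is that the text does not fix the unit of analysis for the primary safety comparison and that its literal wording points to events. The primary and secondary efficacy analyses are untouched. It should be corrected, as a matter of limited weight.

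**What to change.** Amend SAP 3.6 as follows:
- Chi-square or Fisher's exact test compares the number of patients with at least one dental-related AE, with at least one AE overall, and with at least one AE per SOC and PT. The window is the whole study and the denominator is the safety population.
- Define period, or delete the word from the counting rule.
- Report event counts descriptively, or compare them with a model that allows repeats within a patient, such as negative binomial regression.
- Test oral-inspection changes with one record per patient, separately at each inspection.
- State in Table 14.3.1-1 that incidence is tested and frequency is descriptive.

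The cost is a change of wording and table footnotes. The data are the same, and no extra patients or visits are needed.

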6.2.2 Baseline Visit (Week 0)		
893-899	Subgingival debridement will be carried out for all the chosen target implant/s, regardless of the study arm randomization. The Subgingival debridement is the removal of all local irritants from the periodontal pockets and implant surface including the inflammatory tissue. The procedure will be carried out using metal based curettes and ultrasonic management and irrigation with Chlorhexidine ("blasting" cleaning is prohibited).	Subgingival debridement will be carried out for all the chosen target implant/s, regardless of the study arm randomization. The Subgingival debridement is the removal of all local irritants from the periodontal pockets and implant surface including the inflammatory tissue. The procedure will be carried out using metal based curettes and possibly ultrasonic management and/or irrigation with Saline ("blasting" cleaning is prohibited).
918-925	Oral Hygiene instructions - The Investigator or designee will remind the patient of the importance of good hygiene of the mouth (if necessary) and of the restriction of use of Chlorhexidine oral rinses/mouthwashes. In addition the patient will be instructed to refrain from use of toothpicks and/ or in the 24 hours following the chip insertion.	Oral Hygiene instructions - The Investigator or designee will remind the patient of the importance of good hygiene of the mouth (if necessary) and of the restriction of use of Chlorhexidine oral rinses/mouthwashes. In addition the patient will be instructed to refrain from use of toothpicks and/ or floss at least for the 24 hours following the chip insertion, and advised to use such interproximal cleaning devices only to negotiate food impaction for the following 6 days.
928-929		The period between Baseline visit and Visit 3 should not exceed 14 ± 4 days
6.2.3 Visits 3, 4, 5, 6, 7 and 8 (Weeks 2, 4, 6, 8, 10 and 12)		
949	Supragingival Scaling (at week 12 only)	Supragingival Scaling (at week 12 (Visit 8) only).
951-952	Pocket examination and measurements (i.e. PD, R and BOP) only for the target implant/s (only at weeks: 8 and 12)	Pocket examination and measurements (i.e. PD, R and BOP) only for the target implant/s (only at weeks: 8 and 12 (visits 6 and 8)).

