1.2 Design

This study is a multi-center, randomized, single-blind masking, parallel, two-arm clinical study.

The study duration will be 25-28 weeks (6 months) and will comprise a total of 10 visits: Screening and hygienic phase therapy (weeks -3 to -1), Baseline (week 0), week 2, week 4, week 6, week 8, week 10, week 12, week 16 and week 24 (follow up visit).

During the Baseline visit, eligible patients will be randomized to one of the following treatment regimens:

Treatment 1 – Subgingival debridement + Chlorhexidine Gluconate chip (PerioChip®) inserted every fortnight, for the first 12 weeks.

Treatment 2 – Subgingival debridement.

These treatments will be applied for at least 1 (one) and not more than 2 (two) implants in the oral cavity with clinical and radiographical signs of peri-implantitis. Peri-implantitis is defined as marginal bone loss of at least 3 mm from implant shoulder, and at least 2 mm distal and mesial supporting bone left from the apex to the coronal direction, in combination with bleeding and/or suppuration on probing and a peri-implant Probing Depth (PD) of 5-8 mm.

All pocket measurements (PD, BOP and R) and chip insertions will be made in the same order of procedures every time.

The same examiner will perform all the measurements during the study.

The person (physician/hygienist) placing the Chlorhexidine chips in the periodontal pockets or performing the Subgingival debridement, according to the randomization, will not be involved in target pockets measurements (i.e. the examiner and the physician/hygienist placing the chip or performing the Subgingival debridement will be two different persons).

In each patient meeting the entrance criteria, the deepest periodontal pocket of at least 1 (one) and no more than 2 (two) implant/s (if available) will be selected as a target pocket, and will be used for chip/s insertion or Subgingival Debridement and as the primary efficacy end-point.

The target pocket in the selected implant/s, will be treated at each visit with the same treatment arm, initiated at Baseline visit, as described below.

Implant/s which were not selected as target implant/s will be treated as per the investigators discretion as long as it does not affect the study inclusion/exclusion criteria (e.g. treatment with antibiotics or surgery next to a target implant included in the study).

Treatment 1: (PerioChip®)

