Subgingival debridement will be carried out for each one of the target implant which its probing pockets depth (PD of 5-8 mm) were selected as target pockets. The Subgingival debridement procedure will be employ twice: at baseline (visit 2) and after 3 months, at visit 8.

Upon completion of the debridement a PerioChip® will be inserted in each one of the target implant.

PerioChip® contains 2.5 mg Chlorhexidine Gluconate formulated in a biodegradable cross linked gelatine matrix. The maximum dosage for each implant is 5 mg Chlorhexidine Gluconate (i.e. up to 2 PerioChips can be inserted to one implant) and 10 mg of Chlorhexidine Gluconate for each patient per visit. The total number of PerioChips that can be inserted to one patient in one given visit will not exceed 4 PerioChips.

The number of chips inserted to one implant will be a function of the pocket width. In case 2 chips are used in one implant, the insertion will be to the target pocket and the implant surface which is not adjacent to the target pocket (i.e. Buccal - Lingual or Mesial - Distal).

The insertion place should be recorded in the Source Document. All subsequent insertion must be repeated to the exact place chosen in the first insertion procedure.

Treatment 2: (Subgingival Debridement)

Subgingival Debridement will be carried out for each one of the target implant which its probing pockets depth (PD of 5-8 mm) were selected as target pockets.

The Subgingival debridement procedure will be employ twice: at baseline (visit 2) and after 3 months, at visit 8.

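### SAP 3.6 does not split dental AEs by onset, so events from the debridement both arms receive dilute a chip effect that the weeks 2-10 insertions could show more clearly

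*SAP*

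**What the plan says.** SAP 3.6 bases safety on a between-arm comparison: "The primary safety evaluation of the PerioChip® will be performed by comparison to the Subgingival debridement treatment". For dental events it names two measures that serve the same purpose: how many such AEs there are, and the timing of the first, where "the time of first occurrence of dental-related events will be evaluated to assess if the event is associated with the chip insertion". Differences are tested by chi-square or Fisher's exact test. An AE that a subject reports repeatedly in one period counts once, at its worst severity; the SAP does not define the period.

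SAP 1.2 sets the timing. Chips are "inserted every fortnight, for the first 12 weeks". On debridement, for both treatments: "The Subgingival debridement procedure will be employ twice: at baseline (visit 2) and after 3 months, at visit 8". Visit 8 is week 12. The amended text of Protocol 6.2.2 confirms for week 0 that "Subgingival debridement will be carried out for all the chosen target implant/s, regardless of the study arm randomization". In the PerioChip arm the first chip follows at once: "Upon completion of the debridement a PerioChip® will be inserted in each one of the target implant".

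Appendix I lists AE tables by treatment, by system organ class and preferred term, by relationship and by severity. By title, none gives dental AEs by onset interval or time to first dental AE.

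**The concern.** A dental AE just after week 0 or week 12 in the PerioChip arm can come from the debridement or from the chip, since both happen at the same visit. At weeks 2, 4, 6, 8 and 10 only the PerioChip arm has a procedure of this kind. That is the one randomized window in which chip insertion is separated from debridement, and neither measure in SAP 3.6 uses it.

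The total count mixes events from both sources. The time of first occurrence is fixed for a patient once a week-0 event has happened, so later events after chip-only visits add nothing to that measure. At stake is how well the trial can detect dental AEs caused by the chip, and assessing the chip's safety is a stated objective (SAP 1.1).

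**Working it through.** **The plan's figure.** SAP 3.6 states no safety figure. The arm size used here is the 123 per arm of SAP 1.8. It reproduces: for a difference of 0.50 mm, SD 1.30, two-sided 5% and 85% power, the normal approximation gives 122, and the t-test needs 123 (power 85.2%).

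**Inputs from the documents.** Debridement at weeks 0 and 12 in both arms; chips at weeks 0 to 12 every two weeks; hence up to five chip-only insertions. Five is a maximum: the amended Protocol 6.2.3 makes insertion at visit 6 depend on pocket depth and allows it to stop after repeated pop-out at visits 3, 4, 5 and 7.

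**Assumptions (no AE rates in the documents).**
- d = risk of a dental AE after the week-0 debridement, 5% to 50%.
- q = added risk per chip insertion, 2% to 5%.
- Background risk at weeks 2-10, 5% in both arms.
- Risks independent unless stated. Week 12 is left out.

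**Step 1: first event already used up at week 0.** Among patients with a chip-caused event at weeks 2-10, the share who already had a dental AE at week 0 is 1 − (1 − d)(1 − q).

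| d | q = 2% | q = 5% |
|---|---|---|
| 5% | 6.9% | 9.8% |
| 10% | 11.8% | 14.5% |
| 30% | 31.4% | 33.5% |
| 50% | 51.0% | 52.5% |

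The range is about 7% to 53%. If the same patients are prone to both kinds of event (a shared patient effect, SD 1.5 on the logit scale, also assumed), it becomes about 22% to 80%.

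**Step 2: event proportions at d = 30%, q = 2%.**
- Chip-caused event at weeks 2-10: 1 − 0.98^5 = 0.096.
- Any event at weeks 2-10: control 0.05; PerioChip 1 − 0.95 × 0.904 = 0.141.
- First event at weeks 2-10: control 0.70 × 0.05 = 0.035; PerioChip 0.686 × 0.141 = 0.097, where 0.686 = 0.70 × 0.98.
- Any dental AE from week 0 to week 10: control 1 − 0.70 × 0.95 = 0.335; PerioChip 1 − 0.686 × 0.859 = 0.411.

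**Step 3: power at 123 per arm, two-sided 5%.** Power = Φ[(|p1 − p2| − 1.96 × SE0)/SE1], where SE0 uses the pooled proportion and SE1 the separate ones.

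| d, q | Any dental AE | First event at weeks 2-10 | Any event at weeks 2-10 |
|---|---|---|---|
| 5%, 2% | 62% | 64% | 68% |
| 30%, 2% | 23% | 50% | 68% |
| 30%, 5% | 80% | 95% | above 99% |
| 50%, 2% | 13% | 37% | 68% |

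The last column does not depend on d, because the interval excludes week 0. The other two fall as d rises.

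**The case against.** A reader who takes the end of the SAP 3.6 sentence alone might infer that first occurrence is the sole criterion, that later and recurrent events are discarded, and that chip-related events are hidden or cannot be attributed. The documents do not support this.

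- The sentence also names the number of dental AEs.
- The comparator is the debridement-alone arm, debrided at the same visits. A shared debridement peak therefore does not bias the arm comparison; an excess in the PerioChip arm still points to the chip.
- The counting rule collapses repeats only within a period. Later events would be lost from the count only if the period meant the whole study, which the SAP does not say.
- Onset dates and relationship to study drug are kept. Appendix I plans AEs by relationship (14.3.1-3), oral inspection by visit (14.3.3-1), chip insertion by visit (14.3.3-10), and changes in AEs and in dental status since the last visit (14.3.3-11 and -12).
- First events alone retain a signal. With q = 5%, no background, the chip's own week-0 risk ignored, and d = 20%, 30% or 50%, (1 − d) × 0.226 = 18.1%, 15.8% or 11.3% of PerioChip patients have their first event at a chip-only visit, against none in controls. At 123 per arm that is about 22, 19 or 14 patients against 0.
- A cluster of events at week 0 is plausible but assumed.

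All of this stands, and it limits the point to dilution. It does not remove it. A shared control procedure prevents bias but still adds events unrelated to the chip to both arms. The relationship rating does not replace a randomized comparison by onset: the study is single-blind with no placebo chip, so the rating may be made with the arm known, and the documents do not say who makes it. The since-last-visit tables are not, by title, counts of dental AEs by onset.

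**Conclusion.** The point holds as one of lost sensitivity. Both measures in SAP 3.6 mix events at visits where chip and debridement coincide with events at visits where only the chip is given, and no listed table separates them. The size depends on rates that the documents do not give. At a high week-0 risk with a small risk per insertion, the interval comparison raises power materially (23% or 50% to 68%). At a 5% week-0 risk it adds little (62% or 64% to 68%), and at 5% per insertion first events at weeks 2-10 already do well. All figures assume independent risks, five insertions per patient and a 5% background; fewer insertions would lower power on every measure. The change is worth making because it uses the design's only chip-only contrast and costs little.

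**What to change.** In SAP 3.6:

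1. Define the counting period for dental AEs by onset: week 0 to before week 2; week 2 to before week 12; week 12 to before week 16.
2. For each interval, compare between arms the number and percentage of patients with at least one dental AE. Name week 2 to before week 12 as the main assessment of association with chip insertion, and note that both arms are probed at week 8, so control visits are not entirely free of procedures.
3. In the PerioChip arm, report recurrence of the same term after successive insertions.
4. Keep the overall count and the time of first occurrence as supportive. Events from week 16 onward stay in the overall count.
5. Add the matching table to Appendix I.

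The cost is SAP wording and one additional AE table. AE onset dates (SAP 3.6) and visit dates (Listing 16.2.1-2) are already collected, and neither treatment nor visits change.

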1.8 Sample size

A total of 290 patients will be randomized, in order to analyse at least 123 patients for the Subgingival debridement + PerioChip® arm and at least 123 patients for the Subgingival debridement alone arm. Based on the current drop-out rate (after randomization) of 9%, the expected drop-out rate (after randomization) should be between 12%-15%

Based on previous phase IIa studies, the expected drop-out rate in this study will be between 20%-25%. Thus, it is estimated that approximately 375 patients will be screened in order to randomize up to 290 patients.

The sample size is determined based on relevant literature (Machtei et al. 2012) and previous phase IIa study (CLI/013P) that demonstrated substantial improvement (trend toward significant, $p = 0.07$) in PD reduction between PerioChip® and Placebo chip.

The rationale for sample size calculated is based on detecting a difference of 0.50 mm in PD reduction from baseline between PerioChip® and Placebo chip, with 5% statistical significance and 85% power.

A sample size of 123 in each group will have 85% power to detect a difference in means of -0.50 mm (the difference between a Group 1 mean, of -2.29 and a Group 2 mean, of -1.79) assuming that the common standard deviation is 1.30 using a two group t-test with a 0.05 two-sided significance level.

Statistical significance level for all statistical analysis was set to 5%.

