2.4 Categorical

For categorical variables summary tables will be provided giving sample size, absolute and relative frequency and 95% C.I. (Confidence Interval) for proportions by study arm.

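### SAP 3.6 plans a test but no estimate or interval for the between-arm difference in dental-related AEs and tissue changes

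*SAP*

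**What the plan says.** SAP 3.6 sets the primary safety evaluation as PerioChip against debridement: "the number of AEs reported for each treatment group will be compared to see if there is a treatment-related difference in the appearance" of two things, namely dental-related AEs and tissue changes seen at oral inspection. The method for comparing the arms is one sentence: "Chi-square test or Fisher's Exact test will be applied for testing the above differences between the groups". SAP 2.1 fixes the level: "All treatment comparison will be two-sided at the 0.05 level of significance".

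For categorical variables, SAP 2.4 asks for "absolute and relative frequency and 95% C.I. (Confidence Interval) for proportions by study arm". These intervals are within arm. The titles of the 14.3 tables name no between-arm effect measure.

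For efficacy the SAP goes further. Sections 2.1, 3.3.1 and 3.5 give contrasts with 95% intervals from the mixed models. Sections 2.1 and 3.5 give odds ratios with 95% intervals for pocket response and bleeding on probing.

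SAP 3.6 also describes AEs by seriousness, severity, relationship and outcome, and sets the time of the first dental-related event against chip insertion.

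**The concern.** Safety is in the trial's title and is a stated objective, but the sample size rests on pocket depth alone: "A sample size of 123 in each group will have 85% power to detect a difference in means of -0.50 mm". A chi-square or Fisher p-value gives neither the size of a difference nor the increases that the data leave open. Two per-arm intervals side by side do not answer that question either. If dental events are uncommon, a non-significant test is a likely result even when the chip raises their frequency materially. The report would then hold no planned figure showing how large an increase had been excluded.

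**Working it through.** **Inputs from the SAP.** Two-sided alpha 0.05 (2.1). Efficacy difference 0.50 mm, SD 1.30 mm, power 85% (1.8). "A total of 290 patients will be randomized", to analyse "at least 123 patients for the Subgingival debridement + PerioChip® arm and at least 123 patients for the Subgingival debridement alone arm". The safety population equals the ITT population, which is randomised and treated patients (1.4). With equal allocation that is at most 290 / 2 = 145 per arm, and 123 serves as the lower case.

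**Assumed.** The debridement-arm proportion with at least one dental-related AE is in neither document, so a range is used. Each patient is one yes/no outcome. SAP 3.6 counts an AE once per subject and period, which is not quite the same unit.

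**Step 1: the plan's own figure.** n = 2(1.960 + 1.036)² × 1.30² / 0.50² = 121.4, so 122 per arm by the normal approximation. The noncentral t gives 84.9% power at 122 and 85.2% at 123, so 123 is correct. 246 / 0.85 = 289.4, so 290 is also consistent. No power is stated for safety, so nothing stated is numerically wrong.

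**Step 2: power of the safety test for a true doubling.** The approximation, with p̄ the mean of p1 and p2, is

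power ≈ Φ{ [ (p2 − p1) − 1.96 √(2p̄(1 − p̄)/n) ] / √( [p1(1 − p1) + p2(1 − p2)]/n ) }.

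- 10% v 20%, n = 145: (0.1000 − 0.0822) / 0.0415 = 0.43, power 67%.
- 5% v 10%, n = 145: (0.0500 − 0.0606) / 0.0308 = −0.35, power 36% to 37%.

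Exact enumeration over the two binomials (uncorrected chi-square / Fisher) gives:

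| Debridement v PerioChip | 145 per arm | 123 per arm |
|---|---|---|
| 2% v 4% | 15% / 8% | 13% / 6% |
| 5% v 10% | 36% / 29% | 31% / 23% |
| 10% v 20% | 68% / 61% | 61% / 53% |
| 15% v 30% | 87% / 84% | 82% / 77% |
| 20% v 40% | 97% / 95% | 94% / 91% |

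By the approximation, 80% power for a doubling needs 435 per arm at 5% v 10%, 199 at 10% v 20% and 121 at 15% v 30%.

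**Step 3: what an interval would add.** Take an illustrative 14/145 (9.7%) on PerioChip and 7/145 (4.8%) on debridement.

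- Test: pooled proportion 21/290 = 0.0724; z = 0.0483 / √(0.0724 × 0.9276 × 2/145) = 0.0483 / 0.0304 = 1.59; p = 0.11 (Fisher 0.17).
- Wilson limits per arm: 5.8% to 15.6% and 2.4% to 9.6%. They overlap and give no reading of the difference.
- Newcombe limits, in percentage points: 4.83 − √[(9.66 − 5.84)² + (9.63 − 4.83)²] = −1.3 and 4.83 + √[(15.55 − 9.66)² + (4.83 − 2.36)²] = +11.2.
- Risk ratio 2.0, score 95% CI 0.86 to 4.7.

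The p-value says only that the result is not significant. The interval says that an excess of up to about 11 points is not excluded.

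**The case against.** A reader might infer that SAP 3.6 decides safety by a p-value alone and will report a non-significant test as no treatment-related difference. The documents do not support that. No such rule is written, and the test is not the only evidence planned. There are per-arm proportions with intervals, AE tables by relationship and severity (14.3.1-3 and 14.3.1-4), oral inspections by visit, and the timing of first dental events. The planned counts would let anyone compute the risk difference, and SAP 3.1 allows extra tables. The protocol document supplied is a summary of changes, so any fuller safety text in the protocol cannot be checked.

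A reader might also infer that a doubling would generally be missed. That holds only for low control rates, which the documents do not give. At about 15% or more the test usually finds a doubling. Sizing a trial on efficacy alone is ordinary practice and is not an error.

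All of this stands, and it narrows the point to a reporting gap. It does not remove the gap. None of the other planned evaluations estimates the between-arm difference, and a derived interval that is merely possible is not a pre-specified one. It is also fair to say that an upper limit with no margin is not a decision rule. The fix below is therefore one of estimation, not of proof of safety.

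**Conclusion.** The point holds in a limited form. The only formal between-arm method for the primary safety evaluation is a test, and no effect estimate or interval for the difference is planned, while binary efficacy outcomes have both. How much this matters depends on the unknown dental-AE rate. With one yes/no outcome per patient and at most 145 per arm, a doubling from 10% or less has at most about 68% power by chi-square, and 36% from 5%. A doubling from 15% has 87%. No efficacy result and no figure stated in the SAP is affected. This is a cheap improvement that is worth making.

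**What to change.** In SAP 3.6 and Table 14.3.1-1, add the PerioChip-minus-debridement risk difference with a 95% CI (for example Newcombe) for two outcomes: patients with at least one dental-related AE, and patients with a tissue change from baseline at oral inspection. State that the unit for both is the patient, since the present counting rule works by subject and period. Base the between-arm safety statement on the estimate and its interval, including the size of increase that the upper limit leaves open. Keep the chi-square or Fisher p-value as descriptive, and state that p > 0.05 is not evidence of no difference.

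The cost is a paragraph of SAP wording and extra columns in a planned table, from data already collected. Conduct, sample size and alpha do not change. The downside is a less categorical safety statement, because the upper limit will often not exclude a modest increase.
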